**3.0. Research Plan:**

**3.1. Purpose:**

- 1) To randomize 450 participants to 1 of 3 arms: a) a gestational weight gain intervention (GWG-only); b) a postpartum weight loss intervention (PPWL-only), or c) a combined gestational weight gain and postpartum weight loss intervention (GWG+PPWL), and to determine the efficacy of the interventions on GWG as well as PPWL;
- 2) To identify the impact of the interventions on pregnancy-related medical outcomes and health care utilization (from the electronic medical record) and fitness test data (pregravid to 12-month postpartum, from the military fitness database);
- 3) To determine the impact of treatment engagement process data (e.g., session participation, self-monitoring, meal replacement adherence) on intervention outcome.

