**3.3. Significance; 3.4. Military Relevance; & 3.5. Background and Review of Literature:**

Considerable attention has been given to the alarming prevalence of overweight and obesity in the U.S. population [1]. This epidemic extends to women of childbearing age [1], including women who are active duty personnel in the U.S. military and DoD TRICARE beneficiaries (retirees and dependents). As of 2011, 34% of active duty military women were overweight and 6% were obese [2]. Indeed, excess weight is

associated with \$1.1 billion dollars each year in medical costs in the military health care system [3]. Furthermore, specifically for active duty personnel, excess weight and inadequate fitness are frequent causes for discharge. The military must then recruit and train replacements for about \$50,000 per person, thus spending more than \$60 million a year due to failed first-term enlistees [3]. While the long-term impact of pregnancy on military fitness test performance is unknown, several studies have found that women have significantly lower fitness test scores at 6-months postpartum [4, 5]. Finally, pregravid overweight/obesity has been found to be a key risk factor for perinatal complications in both civilian [6] and military populations [7].

In addition to pregravid weight status, excessive gestational weight gain is another key risk factor for pregnancy and delivery complications (e.g., gestational diabetes, preeclampsia, caesarean delivery) [8-11] and negative health outcomes for infants [6, 10, 12] as well as overweight status later in life [11-14]. Excessive gestational weight gain is also associated with postpartum weight retention [15-19], a key concern for the U.S. military. Thus, gestational weight gain is a critical consideration, because it is a modifiable risk factor that can be addressed upon pregnancy confirmation.

Women are not meeting the Institute of Medicine guidelines for gestational weight gain. Recent research indicates that many pregnant women do not gain within the 2009 Institute of Medicine guidelines; specifically, 53-71% of normal weight women, 77-84% of overweight, and 74-83% of obese women exceeded the Institute of Medicine guidelines [20, 21]. Although there is limited research on excessive gestational weight gain among TRICARE beneficiaries, there is some indication that many active duty women, like the civilian population, are exceeding gestational weight gain guidelines [22].

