**PPWL Intervention:** The PPWL intervention will begin at 6-weeks postpartum (when most women will be approved for weight loss and exercise by their obstetrician) for those participants randomized to the PPWL-only or the GWG+PPWL arms, and will continue until 12-months postpartum. The PPWL intervention will provide at least monthly individual, telephone-based sessions (20-30 minutes each), as detailed in Table 2, by trained interventionists. (The number of possible telephone sessions will depend on the level of support needed by each participant to meet her weight loss goals). Similar to the GWG intervention, the PPWL intervention will focus on self-monitoring; weight, dietary intake and exercise goals; and problem solving.

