### 3.6.5. Source of Research Material:

Source of Research Material per Participant (Procedures)	# Routine Care	# Research Driven	# Total Procedures
Research Project Medical Clearance	0	1	1
Screening Visit Interview Questions	0	1	1
Weight	12	7	19
Height	0	5	5
Abdominal Circumference	0	3	3
Contact information	0	7	7
Demographics	0	1	1
International Physical Activity Questionnaire	0	5	5
Breastfeeding Questions	0	2	2
EPDS Depression Screener	3	3	6
Military Fitness Test Scores	0	2	2
Program Evaluation	0	2	2
Modified Pregnancy-Unique Quantification of Emesis and Nausea Index	0	2	2
Weight Gain Recommendations	0	1	1

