- Feeding Practices: Participants will be asked whether their child is being breastfed, partially breastfed (supplemented daily with formula or milk), or fully formula fed and whether solid foods are eaten daily. In addition, the duration of breastfeeding will be assessed. Breastfeeding status will also be used to calibrate postpartum calorie goals.
- Depression: Screening for depression at the first prenatal visit, 28 weeks gestation and at the 6-weeks postpartum visit is standard practice by the WHASC and SAMMC obstetric clinics using the Edinburgh Postnatal Depression Scale. We will obtain these scores from the participants' medical record. In addition, we will assess depression at the 6-weeks, 6-months and 12-months postpartum data collection visit, so we will be able to examine whether our results vary based on the presence of depression.
- Fitness Test Scores: We will obtain the final pregravid and the first postpartum fitness test score from active duty participants to be able to examine the impact of the interventions.
- Program Evaluation: Program satisfaction will be assessed to offer insight into program acceptability as well as barriers and facilitators to participation in each intervention arm. We will adapt the treatment satisfaction measure we are currently using in our "Fit Blue" study to evaluate acceptability and examine feedback on specific intervention aspects, which will inform program refinement and future implementation.
- Medical Outcomes and Health Care Utilization: Pregnancy-related medical outcomes will be obtained from the participant's medical record and will include: maternal (e.g., gestational diabetes, preeclampsia) and fetal conditions; type of delivery; Apgar score; gestational age at delivery; and birth weight and length of the infant. Length-for-age, weight-for-age and weight-for-length Z-scores will be calculated using the Center for Disease Control and Prevention (2000) reference data. Health care utilization (counts of ambulatory visits by type [physician, imaging, lab, other] and hospital/NICU admissions, hospital days) for mother and child will also be captured.

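### Aim 2 covers fitness data to 12 months postpartum, but only the first postpartum score, at an unspecified time, is collected, so the fitness comparison may capture only part of the PPWL intervention

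*Combined protocol and SAP*

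**What the plan says.** Aim 2 in section 3.1 sets out to identify the impact of the interventions on several outcomes, among them "fitness test data (pregravid to 12-month postpartum, from the military fitness database". Section 4 of the summary names military readiness among the things the interventions are meant to improve.

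The collection rule is in section 3.6.8, under Fitness Test Scores: "We will obtain the final pregravid and the first postpartum fitness test score from active duty participants". The procedures table in section 3.6.5 has a row for "Military Fitness Test Scores" with 0 routine, 2 research-driven and 2 in total.

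On the intervention, section 3.6.1 states: "The PPWL intervention will begin at 6-weeks postpartum". It adds that the intervention "will continue until 12-months postpartum".

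Section 3.6 lists fitness scores among the measures obtained at visits up to 12 months, but ties them to no particular visit. The only hint about timing is in the background (sections 3.3 to 3.5), which reports that "several studies have found that women have significantly lower fitness test scores at 6-months postpartum". That describes other studies and is not a rule for this trial. Section 6.0 says in general terms that other measures will be analysed. Section 6.3 gives no model for fitness and does not mention the timing of the test.

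**The concern.** The aim and the collection rule do not cover the same period. The aim reaches to 12 months postpartum, which is also when PPWL ends and when its primary weight outcome is measured (section 6.1). The rule keeps the earliest postpartum score and takes no later one. If a woman tests soon after delivery and again near 12 months, the score that reflects the whole intervention is not collected.

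The background calls the long-term effect of pregnancy on fitness test performance unknown. A first postpartum score taken part-way through PPWL would not fill that gap. Nor could a 12-month weight effect be set beside a fitness effect at the same time. Test dates may also differ between women, and the plan neither asks for the dates nor says how they would be handled.

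**Working it through.** **1. Reproduce the plan's count.** One final pregravid score plus one first postpartum score: 1 + 1 = 2. This matches the total in section 3.6.5, so the wording of section 3.6.8 is not a slip. Two scores are what the plan intends to collect.

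**2. Share of PPWL elapsed at the test.** The start (week 6) and end (12 months, taken as week 52) come from section 3.6.1, so PPWL lasts 52 − 6 = 46 weeks. The test date is not in the documents and is assumed over a range.

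Share elapsed = (week of test − 6) / 46

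| Assumed first test | Week | Share of PPWL elapsed | Weeks left |
|---|---|---|---|
| 3 months | 13 | 7/46 = 15% | 39 |
| 6 months | 26 | 20/46 = 43% | 26 |
| 9 months | 39 | 33/46 = 72% | 13 |
| 12 months | 52 | 46/46 = 100% | 0 |

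**3. What a reduced share could cost (illustration only).** Section 6.2 gives no effect size, SD, alpha or power, so there is no power figure to reproduce. Assume 150 per arm, two-sided 5%, 80% power for the effect at 12 months, and an effect that builds linearly over PPWL. The full effect is then (1.96 + 0.84) × √(2/150) ≈ 0.32 SD, and power at share f is Φ(2.80 f − 1.96).

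- 3 months: 2.80 × 0.152 − 1.96 = −1.53, power about 6%.
- 6 months: 2.80 × 0.435 − 1.96 = −0.74, power about 23%.
- 9 months: 2.80 × 0.717 − 1.96 = 0.05, power about 52%.
- 12 months: 2.80 − 1.96 = 0.84, power 80%.

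Under the same assumed effect, fewer women per arm would lower all of these figures. Only active duty women have scores, section 3.6.7 also admits retirees and dependents, and the active duty number is not given.

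**4. How far the linear assumption matters.** Section 3.6.1 sets a loss of about 1 lb per week until pregravid weight is regained, with a further 5% optional for overweight and obese women. It puts the loss from birth to 6 weeks at about 13 lb. A normal-weight woman who gains the recommended 25 to 35 lb then has 12 to 22 lb to lose, which takes 12 to 22 weeks. At 26 weeks postpartum she has had 20 weeks of PPWL, or 20/22 = 91% of the time needed at the upper end and all of it at the lower end. At f = 0.91, 2.80 × 0.91 − 1.96 = 0.59 and power is about 72%. These are weight goals and not fitness data, but they show that 23% is not a stable figure.

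**The case against.** The strongest reply is that there may be no contradiction. Aim 2's phrase can be read as the window within which two scores are sought, and sections 3.6.5 and 3.6.8 agree on two. That reading is possible and softens the conflict. It still supplies no score near 12 months, and a later score inside the window would go uncollected.

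A second reply is that the timing is assumed. This stands. The documents do not say when participants are tested, and if first tests fall near 12 months the problem disappears. The 6-month figure in the background describes other studies.

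A reader might infer that the data cannot show any PPWL effect on fitness, or that the trial would probably report none. The documents support neither. A test after week 6 can show a partial effect, and randomisation keeps the comparison of arms valid. A reader might also infer that the comparison mostly measures the GWG phase. GWG+PPWL and GWG-only share that phase and differ only in PPWL, so this contrast isolates PPWL whatever the test date.

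Finally, fitness is not a primary outcome. Both hypotheses and the outcomes in section 6.1 concern weight, and fitness scores exist only for active duty women. That limits the weight of the point but does not remove it.

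**Conclusion.** The point holds in a limited form. The stated aim extends to 12 months postpartum, while the plan collects one postpartum score at an unspecified time and no later one. That score may fall before PPWL ends, so the plan may miss the end-of-intervention effect on fitness even where a later score exists.

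The size depends on the test date: 15% of the PPWL period elapsed at 3 months, 43% at 6 months, 100% at 12 months. The 23% power at 6 months is arithmetically correct, but it rests on an assumed test date, linear build-up and a hypothetical 80% starting power. It should be read only as an illustration. An effect that comes early would be diluted much less.

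This should be changed because it concerns a named aim and the remedy is cheap. It does not threaten the primary weight outcomes.

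**What to change.** - **Collection.** Amend section 3.6.8 to extract every official score, with its date, from the last pregravid test through 12 months postpartum, using the military fitness database named in Aim 2. Tests after 12 months fall outside the aim's window and need not be added.
- **PPWL effect.** Use the latest score within 12 months postpartum, with GWG+PPWL versus GWG-only as the contrast, adjusted for pregravid score.
- **GWG effect.** Use GWG+PPWL versus PPWL-only, adjusted for pregravid score, and name in advance which postpartum score serves. GWG-only versus PPWL-only would not do, because after week 6 the comparator is itself receiving PPWL.
- **Timing.** Summarise test timing by arm. Test date arises after randomisation and could be affected by the arm, so adjust for days since delivery only as a sensitivity analysis.
- **Consistency.** Update the count of 2 in section 3.6.5. Reconcile the source of scores: section 3.6.1 has participants hand in a copy, while Aim 2 names the database. Add the fitness analysis to section 6.3.

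The cost is slightly more data handling and these edits to the protocol. No extra participant visit should be needed. For women with only one test by 12 months, nothing changes.

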#### **4.0. Human Subject Protection:**

##### **4.1. Recruitment:**

Participants will be recruited through presentations from research staff and advertisements located in the OB clinics at WHASC and SAMMC as well as other appropriate areas of JBSA. Persons interested in learning more about the study may call the study phone number, or can request a call back or email through the website or in person event. We plan to use flyers, business cards, posters, newspaper, word-of-mouth, and electronic advertisements in base bulletins. Advertisements will include a phone number by which to reach study personnel for more information.

##### **4.2. Consent Processes:**

No study specific procedures will be performed without a written and signed informed consent document and HIPAA Authorization. Participants who do not demonstrate the ability to understand or the willingness to sign the written informed consent document will be excluded from study entry.

#### **4.3 Participation Compensation:**

Subjects will not be paid for participation in this study, however they will receive incentives, such as diapers, diaper ointment, wet bag, and a handprint keepsake for attending data collection visits as described in section 3.6.2.

#### **4.4. Assent Process: N/A**

#### **4.5. Benefits:**

Participants may increase their knowledge about healthy eating and physical activity. However, there is no guarantee or promise of direct benefit for subjects participating in the study.

#### **4.6. Risks:**

All study procedures involve only minimal risks to subjects. Since regular exercise will be encouraged, some people may experience some muscle soreness. There are no major risks associated with taking measurements (height, weight, and waist circumference), taking a health history or collecting questionnaire data. There is, however, the potential risk of loss of confidentiality. Although, we do not anticipate that any study related procedures would increase a participant's risk of suffering from emotional distress or having thoughts of suicide, study procedures are in place so that research staff can respond appropriately if this should occur (see section 4.9 for description of Study Procedures for Distressed Participants).

#### **4.7. Costs: N/A**

#### **4.8. Safeguards for Protecting Information**

The research consents and study related documents will be stored in a locked cabinet in a locked room. All research data including participant demographics will be kept in an electronic database, which will be encrypted, double password protected and the access will be restricted. The research database, consents, and study related documents will be securely maintained for six years after the closure of the study. The research data will not be utilized for further research activity beyond the protocol stipulations without additional IRB approval.

Identifiable research data will be entered electronically into a database housed at UTHSC via a secure connection using Cisco VPN client. The data will be encrypted, double password protected, and access will be restricted. The research database will be managed and maintained at UTHSC. Upon completion of the study protocol, UTHSC will destroy paper forms and links according to IRB procedures.

#### **4.9. Safeguards for Protecting Subjects:**

The principal investigator will be responsible for the protocol safety monitoring. The PI will make study documents readily available for inspection by the local IRB and oversight staff for confirmation of the study data.

Study procedures for distressed participants were developed for research staff to follow in the event that a participant is suffering from emotional distress or having thoughts of suicide.

Several precautions have been taken to both limit the likelihood of participants suffering from a significant psychological event and in the unlikely event that one occurs, we have established appropriate steps for the Counselor to follow in order to get the participant help.

## **A. PRESCREENING FOR DISTRESS**

1. All prospective participants are pre-screened by a military medical provider who both screens the participants in person and reviews their electronic medical record. Specifically, all prospective participants are asked whether they have any “Emotional or psychiatric conditions (depression, schizophrenia)”asked on the *HEALTHY PREGNANCY Research Project Medical Clearance Form*.
2. Additionally, all patients (including the enrolled participants) at OB orientation and at 6-weeks postpartum are administered the 10-item Edinburgh Postnatal Depression Scale (EPDS) as a part of routine pregnancy care. Responses indicating an increased likelihood of depression are addressed by the prenatal care procedures at the medical facility. Please see attached SAMMC Standard Operating Procedure 36 and WHASC Operating Instruction 44-11.
  1. At 6-months and 12-months postpartum the research staff will administer the Edinburgh Postnatal Depression Scale during in-person data collection visits.
    - a. If the participant scores a 10 to 12 on the EPDS, the participant is possibly experiencing depression.
    - b. If the participant scores a 13 or greater on the EPDS, the participant is likely experiencing depression.
    - c. Both these situations should be brought to the attention of a mental health professional.
      - i. Participants will be referred to the Behavioral Health Optimization Program (BHOP) at the WHASC Family Health Clinic. BHOP can be reached by phone at [name]; same-day appointments are also offered.
      - ii. The BHOP service is available to all active duty members. BHOP providers are authorized to document visits in AHLTA so that the encounter notes are available to other authorized users.
  2. If the following response is endorsed by the prospective/enrolled participant, the Counselor will probe briefly for more information about the circumstances of their distress, including potential suicidality.
    - a. Critical responses are:
      - i. Item 10 (“The thought of harming myself has occurred to me”): Responses 1 (“Yes, quite often”) and 2 (“Sometimes”).
    - b. The Counselor will ask whether the participant has a plan to harm herself (to act on her suicidal thoughts) by asking:
      - i. Do you have thoughts about suicide?
      - ii. If yes, do you have a plan to hurt yourself?

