## **A. STUDY PROCEDURES FOR PARTICIPANT DISTRESS, IN-CLINIC OR VIA TELEPHONE**

1. **MILD TO MODERATE DISTRESS (NO THOUGHTS OR INTENT OF HARM TO SELF OR OTHERS)**
  - a. During the in-clinic visits or via telephone, if the participant reports mild to moderate stress (but no suicidal thoughts or morbid ideations such as thoughts of wanting to be dead), the participant will be asked to make an appointment with primary obstetric provider or primary care provider. The patient will also be provided a listing of community resources and encouraged to seek help.
  - b. Counselor will help the participant develop an action plan to be seen by a mental health professional should their distress persist over multiple sessions or worsen.
  - c. Counselor will document the conversation and support materials provided.
  - d. Continued distress without professional assistance and support can be a reason to temporarily or permanently withdraw the participant from the **GWG** or **PPWL** Intervention protocol. Due to safety concerns, notification of withdrawal from the study based on continued distress will result in formal notification of the participant’s command.

2. **SEVERE DISTRESS AND THOUGHTS OR INTENT OF HARM TO SELF OR OTHERS WITH NO INTENT OR PLAN** Participant reports suicidal thoughts or thoughts of harming others but no intent or plan.
  - a. Counselor will develop an action plan to get help from a mental health professional. This conversation with the participant and the action plan will be documented.
  - b. Counselor will follow-up in two business days to ensure that the participant has an appointment with mental health scheduled.
  - c. Counselor will also inform the participant that if their condition worsens the following emergency resources are available:
    - 1) Mental Health Clinic in WHASC (open for Walk-Ins during duty hours: [contact])
    - 2) SAMMC Emergency Department: [contact]
    - 3) Crisis Hotline call: [name]
  
3. **SEVERE DISTRESS AND PLANS OR CLEAR INTENT TO HARM SELF OR OTHERS**
  - a. Participant reports suicidal thoughts or thoughts of harming others and intent or plan.
  - b. Once a participant endorses suicidal intent the counselor will attempt to keep them on the phone.
  - c. Whether the Counselor – Participant contact is by phone or in-person, the Counselor will attempt to maintain contact with the participant, identify the location of the Participant and maintain verbal contact until help arrives.

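### After a critical EPDS item 10 response, the scripted questions never ask about intent, although intent without a plan is enough for the emergency response

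*Combined protocol and SAP*

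**What the plan says.** Section 4.9, Prescreening for distress, treats the two most frequent of the affirmative answers to EPDS item 10 (thoughts of harming herself) as critical. After one of these, "the Counselor will probe briefly for more information about the circumstances of their distress, including potential suicidality". Item 2.b then gives the follow-up: "The Counselor will ask whether the participant has a plan to harm herself (to act on her suicidal thoughts) by asking". Two questions come next. The first asks about thoughts of suicide. The second is conditional on the first: "If yes, do you have a plan to hurt yourself".

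The procedures for participant distress, in the same section, sort cases into levels by what the woman reports. The body text of level 2 is "Participant reports suicidal thoughts or thoughts of harming others but no intent or plan". Level 3 is "Participant reports suicidal thoughts or thoughts of harming others and intent or plan".

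The responses differ in kind. At level 2, "Counselor will develop an action plan to get help from a mental health professional", "Counselor will follow-up in two business days to ensure that the participant has an appointment with mental health scheduled", and she is told whom to contact if things get worse. At level 3 the Counselor tries to establish where she is and to stay in contact with her until help comes, while a colleague calls the emergency number.

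**The concern.** Levels 2 and 3 are separated by two criteria, intent and plan, and either one is enough for level 3. The script asks about only one of them. If nobody asks about intent, a Counselor can take silence as absence and settle on level 2. For a woman who intends to act but has formed no plan, the emergency response may then not start. This is a participant-safety matter; no endpoint, estimate or test is affected.

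Two wording faults lie close by. Item 10 concerns self-harm, but the plan question is reached only through a yes to suicide. And the level 2 heading names intent of harm as a feature of the level and then, in the same line, says that there is no intent or plan.

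**Working it through.** No arithmetic applies, and the plan states no figure on this point to reproduce. The check sets the scripted questions against the level definitions.

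Inputs, all from section 4.9:
- Set question i: suicidal thoughts, yes or no.
- Set question ii: plan to hurt herself, asked only if i is yes.
- Level 2 body text: thoughts, with neither intent nor plan.
- Level 3 body text: thoughts, with intent or plan.

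The possible cases after a critical item 10 response, assuming truthful answers to the set questions alone:

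| Suicidal thoughts | Intent | Plan | Answers to i, ii | Level by definition |
|---|---|---|---|---|
| yes | no | no | yes, no | 2 |
| yes | yes | no | yes, no | 3 |
| yes | no | yes | yes, yes | 3 |
| yes | yes | yes | yes, yes | 3 |
| no | any | any | no, not asked | not settled by the script |

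1. Rows one and two give identical answers and belong to different levels. A yes to thoughts with a no to a plan leaves intent unknown, so the set questions cannot separate level 2 from level 3 for these women.
2. Rows three and four are placed correctly whatever the intent. The gap is confined to intent without a plan.
3. In the last row the woman has already endorsed thoughts of harming herself. The stem of 2.b is unconditional, but the wording of question ii skips the plan question for her. The level 3 heading speaks of harm to self while its body text speaks of suicidal thoughts, so her placement is unclear, and the script does not collect the answer that would help.
4. The open probe comes before the set questions. It names the circumstances of distress and possible suicidality, but not intent. It can reveal intent; it does not require the question.
5. The parenthesis in the stem, about acting on her thoughts, comes close to intent. It describes the purpose of asking, however, and the words to be spoken ask about a plan.

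**The case against.** The strongest reply is that the protocol already requires intent to be established. Level 2 applies only where intent is absent, so a Counselor who assigns it without knowing has departed from the text. Level 3 also treats endorsement of suicidal intent as a trigger in its own right. This stands, and it sets the limit of the point: what is missing is a prompt, not a criterion or a response. A reader might infer that the plan has no route to emergency care for intent without a plan. That is not so: a Counselor who draws out intent in the probe would place the woman correctly.

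Staff training may also fill the gap. Section 3.6.1 says that interventionists hold degrees in fields such as counseling, psychology, social work and nursing. But the visible text does not say that the Counselor is one of them, or is a mental health professional.

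The score-based referral is a partial backstop. A total score of 10 or more at 6 or 12 months leads to a referral, with same-day appointments offered. It depends on the total rather than on item 10, it is not an emergency response, and the service is described as available to active duty members, whereas section 3.6.7 also admits retirees and dependents. Level 2 itself is not empty either: "Counselor will also inform the participant that if their condition worsens the following emergency resources are available".

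Finally, the clinic procedures cited in section 4.9 and the Data Safety Monitoring Plan listed in section 13 cannot be read here. The clinic procedures are cited for responses in routine-care screening, not for the Counselor's set questions, but any of these documents might add a question on intent.

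**Conclusion.** The point holds in a narrow form: the visible script omits one of the protocol's own two deciding criteria, so intent without a plan can be handled as level 2 unless the probe or the woman's own account reveals it. A self-harm answer combined with a denial of suicidal thoughts skips the plan question as worded. This is a cheap improvement to participant safety. It rests on the wording of section 4.9 alone and on the assumption that no unseen attachment supplies the missing question.

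The size cannot be given as a frequency. The documents report no rate of critical item 10 responses and none of intent without a plan.

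Three stronger readings are tempting and not supported:
- A reader might multiply participants by screens to bound the exposure. Section 3.6.5 lists 3 research-driven and 3 routine EPDS per participant, while section 4.9 has research staff giving it at 6 and 12 months only. The count depends on which screens are meant, and screens are not critical responses.
- A reader might infer that thoughts of harming others are misplaced at level 2 by the same route. Those thoughts appear in both level definitions and in neither question, but the trigger is a self-harm item, and the route described does not lead there.
- A reader might infer that unclear intent should count as level 3. The level 3 heading asks for clear intent, and the level starts emergency calls. Sending every ambiguous answer there would be a policy choice, not a correction.

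**What to change.** In section 4.9, Prescreening for distress, item 2.b:
- add a set question on whether she intends to act on her thoughts;
- ask the intent and plan questions after any critical item 10 response, not only after a yes to suicide.

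In the distress procedures, reword the level 2 heading to match its body text: thoughts, with no intent or plan.

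The cost is a short wording amendment and brief training of the staff who give the EPDS and ask the follow-up questions. Section 3.6.2 has measures taken by staff blinded to arm, so those staff should be trained apart from the weekly meetings of interventionists and investigators described under Treatment Fidelity in section 3.6.1. There may be a few more emergency responses; their number cannot be estimated from the documents. The sample size and analysis do not change.
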